The following amendments and/or administrative changes have been made to this protocol since the implementation of the first approved version.

Amendment No.	Protocol version no.	Date issued	Summary of changes made since previous version
Substantial (Amendment 4)	2.0		
 1. Change in Site PI and Co-Investigators 2. Changes in CTR team 3. Added COVID related background. 4. Change to risk stratification for high NEWS (≥ 7) and low PCT (< 0.05) to moderate risk. 5. Consent process altered in section 9.3 6. Added planned stratification of all outcomes by COVID-19 diagnosis 7. It should read "low PCT (< 0.5)" rather than "low PCT (< 0.05)" 8. Added Covid to the list of variables to be collected. 9. Added COVID diagnosis to table 1. 10. Added witness consent to Qualitative interviews. 11. Subgroup and interim analysis updated.
Non-substantial (Amendment 18)	2.1		
 1. Updated final decisions on primary effectiveness (section 5.3). Decreased mortality with same or

Substantial (Amendment 23)
	
3.0
		
equivalent antibiotic initiation changed from 'unclear effect' to 'Effective'.
 
 1. Inserted website information for randomisation, 2. Updated research administrator at CTR. 3. Updated qualitative researchers at CTR. 4. Updated planned number of sites (Section 2) 5. Updated planned trial period (Section 2). 6. Number of sites updated in setting information (Section 6.2). 7. Updated information on the trial intervention to include PathFast BRAHMS PCT reader (section 10)
---	------------	--	--

2 Synopsis

Short title	PROcalcitonin and NEWS2 evaluation for T imely identification of sepsis and O ptimal use of antibiotics in the Emergency Department
Acronym	PRONTO
Internal ref. no.	UoL001520
Development phase	Phase III
Funder and ref.	NIHR HTA (ref 17/136/13)
Trial design	Prospective, individually randomised, open label, two arm, group sequential RCT
Trial participants	Adults and adolescents ≥ 16 years presenting to emergency care departments with suspected sepsis.
Planned sample size	7676
Planned number of sites	Maximum of 20 sites
Inclusion criteria	Patients ≥ 16 years presenting to the ED with suspected sepsis
Exclusion criteria	
 • Currently on intravenous (IV) antibiotics • Current use of any chemotherapy agent associated with myelablation/suppression. • History of solid organ transplantation, allogeneic bone marrow or stem cell transplantation within 3 months prior to consent. • Patients requiring urgent surgical intervention. • Presence of an advance directive to withhold life-sustaining treatment (patients not wishing to receive Cardiopulmonary Resuscitation (CPR) may qualify provided they receive all other resuscitative measures e.g. respiratory support, fluid resuscitation).
Treatment duration	As determined by treating clinician
Follow-up duration	To 28 days (primary endpoint) and 90 days.
Planned trial period	1st December 2019 - 30 th April 2024
Primary objective	To assess whether the addition of Procalcitonin (PCT) measurement to NEWS2 scoring leads to a reduction in IV antibiotic initiation with no increase in 28-day mortality compared to NEWS2 scoring alone in the management of patients seen in the Emergency Department (ED) with suspected sepsis.
Secondary objectives	The assessment of a) feasibility, b) cost-effectiveness and c) acceptability to patients and their family.
Tertiary/Exploratory objectives	N/A
Primary outcomes	
Co-primary outcomes:
 
 • IV antibiotics initiation at 3 hours (superiority endpoint) • Mortality at 28 days (non-inferiority endpoint). 
A positive conclusion will be drawn only if both a decrease in IV antibiotic initiation AND non-inferiority in mortality are demonstrated.

Secondary outcomes	
 • Total duration of all antibiotics (IV and oral) within 28 days of recruitment • Type of antibiotic • Readmissions • Antibiotic associated side effects • Health utility (EQ-5D/5L) at 90 days. • Feasibility of implementing PCT testing alongside NEWS2 scoring in Emergency Departments (EDs)

	
 Acceptability of implementing PCT testing alongside NEWS2 scoring in EDs, to patients, carers and clinicians
Tertiary/Exploratory outcomes	N/A
Intervention	The addition of point of care testing for PCT to NEWS2 scoring compared to current standard of care using NEWS2 alone.

3 Trial summary & schema

[figure not shown]

Figure 1. Participant Flow Diagram

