5.3 Primary outcomes measure(s)

The study will use the following as co-primary outcomes:

- Intravenous antimicrobial initiation – binary outcome assessed at 3 hours.
- 28-day mortality – binary outcome.

Final decisions about the primary effectiveness, using these co-primary outcomes will be made based on:

	Reduced antibiotic initiation	Same or more antibiotic initiation
Decreased mortality	Effective	Effective
Equivalent mortality	Effective	Not effective
Increased mortality	Not effective / harmful	Not effective / harmful

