16.2 Sample size

The sample size calculation is based on two co-primary outcomes [36] :

1. 28-day mortality, for which we want to show non-inferiority of the PCT guided assessment as compared to current standard practice, using an absolute 2.5% non-inferiority margin. Assuming a 28-day mortality of 15% in patients managed as suspected sepsis treated in the ED [3, 12], this means that any increase in 28-day mortality from 15% to not more than 17.5% would be considered non-inferior. For

90% power and one-sided 5% significance level the sample size required is 7002, assuming there is no difference in 28-day mortality between arms. Our patient focus group were also consulted on the 2.5% non-inferiority margin and felt that this was acceptable if there were mechanisms to monitor trial outcomes, and if this was what was needed to provide a sample size which would ensure the trial could be completed as well as answer the research question.

2. Initiation of antibiotics treatment, for which we want to show superiority. Currently around 90% of patients managed as suspected sepsis receive antibiotics (RLBUHT, unpublished data). A reduction by 10 percentage points to 80% would be considered a success. To detect such an effect with 90% power and two-sided 5% significance level the sample size required is 532, which is substantially lower than what is needed for the non-inferiority endpoint. With 7002 patients we would be able to detect effects as small as a reduction from 90% to 87.6% prescriptions, with 90% power.

Accounting for 5% dropout, we need a total sample size of 7372. We include one interim analysis (after 50% of patients have provided data) with options to stop the trial early using group-sequential O'Brien-Fleming boundaries [37, 38]. We will consider stopping for effectiveness if:

- the PCT guided assessment is superior in terms of 28-day mortality (i.e. a significant reduction to less than 15%), or
- the PCT guided assessment is non-inferior in terms of 28-day mortality and superior in terms of initiation of antibiotics.

We will consider stopping for futility if the results of the interim analysis suggest futility for both endpoints.

The group-sequential design will increase the total maximum sample size (if the study is not stopped after the interim analysis) by just over 4% to 7676 (inflated for 5% dropout). However, the sample size will be substantially smaller if the trial does get stopped early.

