17.1 Main analysis

The primary analysis will be intention to treat and will fit separate two-level logistic regression models (patients nested within sites) to both primary outcomes (antibiotic initiation and mortality), controlling for baseline NEWS2 score (minimisation factor). The intervention will be considered effective if there is both a significant reduction in antibiotic initiation AND if the difference in mortality between the two group is negligible (i.e. non-inferior). (See section 5.3 for the primary outcome for effectiveness table which includes antibiotics and mortality outcomes.)

A planned interim analysis of the co-primary outcomes will be conducted when 50% of patients have been recruited and followed up for 28 days. Stopping the study shall be recommended by the IDMC based on group-sequential O'Brien-Fleming boundaries [37, 38]. They shall recommend stopping for effectiveness if:

- the PCT guided assessment is superior in terms of 28-day mortality (i.e. a significant reduction to less than 15%), or
- the PCT guided assessment is non-inferior in terms of 28-day mortality and superior in terms of initiation of antibiotics.

They shall recommend stopping for futility if the results of the interim analysis suggest futility for both endpoints.

In case the 28-day mortality rate in the control arm deviates from the assumed 15%, the absolute 2.5% non-inferiority margin will be replaced with an arcsine difference 'non-inferiority frontier' [39].

The final primary analysis will be adjusted to account for the interim analysis. Imputation of missing data will be done as part of sensitivity analyses.

In a secondary analysis, complier adjusted causal effect models will be fitted to allow for non-adherence to the intervention. Two models will be fitted allowing for two different definitions of adherence:

1. Patients randomised to PCT guided care in whom a PCT test is done and the clinician considers the results as part of their decision making.
2. Patients randomised to PCT guided care in whom a PCT test is done and the clinician follows the algorithm exactly.

All secondary analysis will also be performed based on intention to treat and utilising two level models to allow for patients nested within sites. The following analyses will be undertaken (Table 3):

Table 3: Planned outcomes and analyses

Outcome	Measure	Time frame	Analysis
Antibiotic initiation	Time until initiation	In ED	Cox regression

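### The synopsis requires both co-primary conditions for a positive trial, but the Section 5.3 decision table and the interim rule also accept lower mortality alone

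*Protocol*

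**What the plan says.** Four places in the Protocol bear on what makes the trial positive.

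- **Section 2, Synopsis (primary outcomes):** "A positive conclusion will be drawn only if both a decrease in IV antibiotic initiation AND non-inferiority in mortality are demonstrated". This makes both conditions necessary.
- **Section 5.3:** "Final decisions about the primary effectiveness, using these co-primary outcomes will be made based on" a table of mortality result against antibiotic result. Its first row reads "Decreased mortality Effective Effective", so a mortality decrease is rated effective in both antibiotic columns, including the one for no reduction.
- **Sections 16.2 and 17.1, interim analysis:** stopping for effectiveness is open if "the PCT guided assessment is superior in terms of 28-day mortality (i.e. a significant reduction to less than 15%), or" if mortality is non-inferior and antibiotic initiation is superior. Either route suffices.
- **Section 17.1, final analysis:** "The intervention will be considered effective if there is both a significant reduction in antibiotic initiation AND if the difference in mortality" is negligible, meaning non-inferior. The next sentence adds: "See section 5.3 for the primary outcome for effectiveness table which includes antibiotics and mortality outcomes".

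On significance levels, Section 16.2 gives one-sided 5% for mortality non-inferiority and two-sided 5% for antibiotic superiority. It gives none for mortality superiority.

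**The concern.** A rule that requires both conditions cannot stand beside a table that accepts one of them alone. The two differ in exactly one cell: mortality lower, antibiotic initiation not reduced. For that result the table gives a positive verdict and the synopsis a negative one. The trial could also stop early for effectiveness on a result that the synopsis does not count as positive.

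If the conflict stays, the choice between the rules could be made after the data are seen. The mortality-alone route is also a second way to succeed, so the error rate of the whole decision depends on the level at which that route is tested.

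**Working it through.** **Inputs (Protocol Section 16.2).** Control mortality 15%; margin 2.5 points; one-sided 5% and 90% power for non-inferiority; antibiotic initiation 90% against 80% at two-sided 5% and 90% power; 7002 before dropout; 5% dropout; maximum 7676. Allocation is 1:1 (Section 6.1).

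**Assumptions.** Mortality superiority is tested at one-sided 2.5% or one-sided 5%, since the protocol gives no level. The endpoints are independent in the analytic work.

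**Step 1: reproduce the plan's figures.**
- Non-inferiority: n per arm = (1.645 + 1.282)² × 2 × 0.15 × 0.85 / 0.025² = 3495, total 6990 (stated 7002).
- Antibiotics: n per arm = [1.960 × √(2 × 0.85 × 0.15) + 1.282 × √(0.9 × 0.1 + 0.8 × 0.2)]² / 0.10² = 266, total 532 (stated 532).
- Dropout: 7002 / 0.95 = 7371 (stated 7372). A two-look O'Brien-Fleming design that stops for efficacy or futility has an inflation factor of 1.043, giving about 7690 (stated 7676).

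The planning figures reproduce closely.

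**Step 2: one data set, two verdicts.** Analysed per arm: 7676 × 0.95 / 2 = 3646. Take mortality 15.0% (control) and 12.5% (PCT), and antibiotics 90% in both arms. SE = √[(0.15 × 0.85 + 0.125 × 0.875) / 3646] = 0.0081. The difference is −2.5 points, 95% CI −4.1 to −0.9. This is effective under 5.3 and not positive under the synopsis.

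**Step 3: probability of an effective verdict, fixed design with 3501 per arm.**
SE = √(2 × 0.15 × 0.85 / 3501) = 0.00853, and 0.025 / 0.00853 = 2.929. Let *d* be the true mortality difference, *b* the probability that antibiotic superiority is shown (0.025 if there is no effect), and *z* the critical value for mortality superiority.
- P(NI) = Φ((0.025 − d)/SE − 1.645)
- P(S) = Φ(−d/SE − z)
- Both-conditions rule: P(NI) × b
- 5.3 rule: P(NI) × b + P(S) × (1 − b), because mortality superiority implies non-inferiority

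| Truth | Both conditions | 5.3, superiority at one-sided 2.5% | 5.3, superiority at one-sided 5% |
|---|---|---|---|
| Mortality −2.5 points, no antibiotic effect | 1.000 × 0.025 = 2.5% | 0.025 + 0.834 × 0.975 = 84% | 0.025 + 0.9005 × 0.975 = 90% |
| No effect on either | 0.9005 × 0.025 = 2.25% | 0.0225 + 0.025 × 0.975 = 4.7% | 0.0225 + 0.05 × 0.975 = 7.1% |
| Mortality +2.5 points, real antibiotic reduction (b = 1) | 5.0% | 5.0% | 5.0% |

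**Step 4: add the interim look.** Two million simulated trials with O'Brien-Fleming boundaries at both looks, 7676 × 0.95 analysed, non-binding futility and endpoint correlation from −0.2 to 0.2 gave the following with no effect on either outcome:
- both-conditions rule: 1.9% to 2.4%
- 5.3 rule: 4.5% to 4.7% (one-sided 2.5%) or 6.9% to 7.1% (one-sided 5%)
- mortality-alone route at the interim only, both conditions at the end: 2.2% to 2.6% or 2.8% to 3.2%

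**The case against.** Four objections deserve an answer.

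**The governing text can be identified.** Section 5.3 says that final decisions rest on its table, and the amendment history shows that the cell in question was set to its present value on purpose. The synopsis line may simply not have been updated. This is a good reason to prefer one repair over the other, but the current sections still disagree.

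**Section 17.1 does not conflict with 5.3.** A reader might take 17.1 as a second statement that both conditions are necessary. The text does not support that. It gives the two conditions as sufficient (*if*, not *only if*) and then refers to the table. This objection stands: the clear conflict is between the synopsis on one side and 5.3 and the interim rule on the other.

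**The interim rule governs stopping, not success.** Stopping on a mortality benefit can coexist with a narrower definition of a positive trial. That is so, but the protocol calls it stopping for effectiveness, and under the synopsis the stopped trial would not be positive.

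**Error inflation is not shown.** A reader might infer from the second route that the false-positive rate is uncontrolled. The only level that the protocol gives for a superiority test is two-sided 5%. Used for mortality, it keeps the chance of a false verdict with no effect on either outcome at or below 2.5% + 2.5% = 5%, whatever the correlation. The both-conditions rule itself reaches 5% at its worst point, so setting its 2.25% against 7.1% is not like for like. The SAP, which is not at hand, may fix the level. This objection stands.

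**Conclusion.** The contradiction is real and lies in the current text. It decides the primary conclusion whenever mortality falls and antibiotic initiation does not. In that case (true difference −2.5 points, no antibiotic effect) the chance of an effective verdict is 2.5% under the synopsis and 84% to 90% under 5.3. These figures assume 15% mortality for the variance, 3501 per arm, a fixed design and independent endpoints.

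The protocol sets no level for the mortality-alone route. With no effect on either outcome, that route takes the probability of an effective verdict from about 2.25% to 4.7% at one-sided 2.5%, or to about 7.1% at one-sided 5%. Only the second exceeds 5%, and nothing in the protocol assigns it to a superiority test.

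A reader might also take the 15% in the interim rule as a fixed comparator for the PCT arm. The documents do not support that: Section 17.1 compares the arms by two-level logistic regression, and no one-sample test is specified. The phrase is loose, the more so because 17.1 allows for a control rate other than 15%, but it is a point of wording and not a demonstrated error.

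**What to change.** State one rule, in the same words, in the synopsis and Sections 5.3, 16.2 and 17.1.

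- **Simplest, because 5.3 is the governing table:** add the mortality-superiority route to the synopsis and to the effectiveness statement in 17.1. Test it after non-inferiority has been shown, against the concurrent control arm, at two-sided 5%, with its own O'Brien-Fleming boundary. State the resulting probability of an effective verdict with no effect on either outcome: about 4.7%, at most 5%.
- **Alternative:** keep the both-conditions rule everywhere and relabel the 5.3 cell as a mortality benefit with the primary question not met. The interim rule should then say that stopping on mortality alone is not a positive primary conclusion.

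In either case, replace the reference to 15% in the interim rule (16.2 and 17.1) with a comparison against the concurrent control arm. The cost is protocol wording, carried through to the SAP, the interim SAP and the IDMC charter. Sample size and data collection do not change.

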3.1 Trial lay summary

Sepsis is a common, potentially life-threatening complication of infection. The optimal treatment for sepsis includes early recognition, prompt antibiotics and fluids into a vein (intravenous/IV). Currently, clinicians assess severity in patients in the Emergency Department (ED) with a scoring system based on simple to measure observations: the National Early Warning Score (NEWS2). NEWS2 helps clinicians identify the sickest patients. It is not specific and tends to over-diagnose sepsis leading to over-prescribing of antibiotics and promoting antimicrobial resistance. It is the best we have and currently used in over 70% of English hospitals. Adults with suspected sepsis fall into one of three categories: a) those looking ill needing urgent IV antibiotics and fluids within 1 hour, b) those that are unwell, but will not come to harm if IV antibiotics are not administered within 1 hour, allowing time for further assessment prior to starting antibiotics within 3 hours if required, c) those not critically unwell who may or may not need IV antibiotics. Procalcitonin (PCT), a blood test not widely used in the NHS, helps to identify bacterial infection. The National Institute for Health and Care Excellence (NICE) recommended further research on PCT testing in EDs for guiding antibiotic use in people with suspected sepsis.

In this study, we will conduct a randomised controlled trial to compare PCT-supported assessment with standard care of suspected sepsis in adults presenting to the ED, and measure whether this approach reduces prescriptions of antibiotics without increasing mortality by decreasing uncertainty in the group who may not need IV antibiotics urgently within 1 hour, or not need antibiotics at all.

Ten to 14 hospitals will take part in the study and 7676 adult patients with suspected sepsis will be randomly assigned to current standard of care or PCT-supported care. In the PCT arm, a bedside test (taking 20 minutes) is performed plus the NEWS2 assessment. Depending on the result of the PCT plus the NEWS2, patients will receive IV antibiotics and fluids within the current recommended time frame depending on severity (see Figure 1 – participant flow diagram). Doctors and patients will know what treatment arm they are in. Doctors remain free to use antibiotics outside the study guidelines using their clinical judgement in any of the

risk groups. The key outcome measures will be whether IV antibiotics are started, and death within 28 days. An analysis will be done to understand how well clinicians follow the recommendations, ease of use of the additional test in a busy ED, and its cost effectiveness. A sample of patients interviewed at 90 days follow up will assess experiences of care.

4 Background

Sepsis is defined as life-threatening organ dysfunction caused by a dysregulated host response to infection [1] and is a medical emergency requiring prompt antimicrobial therapy and physiological support. The identification, assessment and management of sepsis is challenging because of its many non-specific symptoms and signs, which can be caused by both infectious and non-infectious diseases. In line with international recommendations, National Institute for Health and Care Excellence (NICE) sepsis guidelines suggest the administration of intravenous antibiotics within an hour to patients displaying features considered to be high risk for ICU admission and death [2]. However, up to 50% of patients initially managed as sepsis in the Emergency department (ED) do not have a final diagnosis of sepsis [3, 4]. The current approach leads to overuse of antibiotics with the associated risk of antimicrobial resistance (AMR). For example, since introduction of the National Commissioning for Quality and Innovation (CQUIN) for sepsis in 2015, intravenous broad spectrum antibiotic use in Emergency Departments has increased by 83% over 3 years [5].

Use of antibiotics brings its own problems including antibiotic-related adverse drug reactions (e.g. *C. difficile* infection) [6], extended hospital stays, and generation of antimicrobial resistance with increased long term adverse consequences to health care. There is some evidence that unnecessary use of broad spectrum antibiotics increases the risk of developing sepsis within 90 days of a previous hospital stay [7]. The O'Neill report on antimicrobial resistance suggests that there are about 1 million deaths a year as a result of AMR and this is likely to rise to an estimated 10 million by 2050 [6]. One of the key recommendations was to promote new, rapid diagnostics to improve accuracy of early diagnosis and cut unnecessary use of antibiotics.

NICE guidelines recommending antibiotics within one hour [2] must be balanced against NICE antimicrobial stewardship guidelines and the Department of Health (DoH) antimicrobial stewardship toolkit that recommend antimicrobials should not be started unless there is clear evidence of infection [8]. Clinical decision support is essential to balance these competing drivers. Patients in our patient and public involvement (PPI) workshop described this situation as *“it seems to me you are damned if you do – damned if you don’t because medical professionals won’t want to take a chance and the public will be quick to complain – at the moment where there is a gap in knowledge everyone will err on the side of caution.”* For similar reasons, a group of clinicians have launched a counter campaign against the surviving sepsis campaign guidelines which recommends antibiotics within 1 hour for all patients with suspected sepsis. They argue that it risks overtesting and overtreating patients with low probability of sepsis, diverting attention away from more evidence-based time-sensitive tasks and patients who require more urgent treatment (<https://www.jwatch.org/na46999/2018/08/06/surviving-sepsis-campaign-rush-judgment>).

In the busy environment of an ED or Acute Medical Unit (AMU), risk stratification currently relies on NICE sepsis guidelines and the National Early Warning Score (NEWS2) assessment based on six vital signs and requirement for supplemental oxygen [9]. The challenge of delivering high quality sepsis care in an ED setting has been well recognised [10, 11]. Accurate risk stratification could improve antimicrobial stewardship where clinical teams feel confident that they can safely assess and wait for results of initial investigations prior to commencing antibiotics within 3 hours, but not within the 1 hour target. The use of screening tools for sepsis within EDs in the UK remains a point for discussion. The third international consensus definition (Sepsis 3) recommended use of a new, rapid scoring tool, the quick Sequential Organ Failure Assessment (qSOFA) score, to identify patients at high risk of death and prolonged ICU stay [1]. A qSOFA ≥ 2 is used as an indicator of screening tool for sepsis. Current NHS England policy is for NEWS2 score to be adopted by all hospitals in England by April 2019 in order to facilitate detection of deterioration and sepsis [9]. NEWS2 has been demonstrated to have comparable diagnostic accuracy in detection of severe outcomes and is more widely used in the NHS than qSOFA [12, 13]. NHS England recommends that if a NEWS2 ≥ 5 is accompanied by suspicion of sepsis, this should prompt the senior clinical decision-maker,

using clinical judgment, to start appropriate treatment (intravenous antibiotics and fluids), as indicated, within an hour of the risk being recognised. A NEWS2 ≥ 5 rather than qSOFA ≥ 2 (which is more comparable to NEWS2 ≥ 7) as threshold for the screening for sepsis reduces specificity and increases the number of patients considered to be in a high risk group from approximately 20-25% to 50-75% [unpublished RLBUHT data]. Several further evaluations of alternative scoring systems including a retrospective cohort study from our hospital [12] have concluded that whilst differences in the scoring systems exist, no scoring system has both high sensitivity and specificity for predicting adverse outcomes in sepsis in the ED, and NEWS2 is more accurate than qSOFA for predicting adverse outcomes.

The emergence of COVID-19 has exacerbated this previously highlighted problem. COVID-19 is a viral infection which presents within the sepsis syndrome constellation and is unresponsive to antibacterials. NEWS2 scores are broadly predictive of COVID-19 outcome on presentation [14], although there are some concerns on its ability to identify unwell patients with high oxygen requirements [15]. Secondary bacterial infections are uncommon at presentation to A&E (3.5%) [16], despite this up to 83% of patients with COVID-19 received antibiotics [16, 17]. NEWS2 in COVID-19 does not appear to have an association with bacterial co-infection at presentation. Initial investigations in the ED can be helpful in distinguishing between COVID-19 and bacterial pneumonia including typical radiographic changes, lymphopenia, and increasingly COVID-19 point of care diagnostics [18]. These results would be available within 3 hours for assessment and could potentially reduce unnecessary antimicrobial usage in COVID-19 management. Presentations with COVID-19 have much reduced since the peak in April 2020, but continued cases are expected for the foreseeable future. COVID-19 will therefore become part of the differential diagnosis in undifferentiated sepsis presenting to EDs and therefore a prime target for PRONTO .

Procalcitonin (PCT) is a reliable biomarker that changes early in the course of bacterial infection. A recent Cochrane meta-analysis [19] demonstrated that the use of PCT to guide antibiotic treatment in patients with acute respiratory infections reduced antibiotic exposure and side-effects, and improved survival. Procalcitonin is currently the biomarker with the

most available evidence to identify bacterial infections and antibiotic prescription decisions. PCT is predictive of outcome in COVID-19 cases and this may be because of its ability to identify superadded bacterial infection [20, 21]. It may also be a useful tool for antibiotic stewardship [22]. It has been used to differentiate viral from bacterial pneumonia prior to COVID-19. The available evidence suggests a low PCT will have good negative predictive value for a bacterial infection in cases of COVID-19 [23].

This trial addresses research recommendations from three separate NICE guidelines; Sepsis recognition, diagnosis and management (NG51) [2], PCT testing for diagnosing and monitoring sepsis (DG18) [24] and Antimicrobial stewardship: systems and processes for effective antimicrobial medicine use (NG15) [25]. In addition, it is ideally placed to address the research recommendations from NICE COVID-19 rapid guideline: antibiotics for pneumonia in adults in hospital (NG173) on the utility of PCT in COVID-19 pneumonia [26]. It will help to determine if NEWS2 in combination with PCT can improve the recognition and risk stratification of undifferentiated sepsis including COVID-19, and facilitate prompt and appropriate antibiotics in adults presenting to the ED. It will also determine the clinical and cost effectiveness of PCT point-of-care tests in the ED for the diagnosis of sepsis. NICE antimicrobial stewardship guidelines recommend the use of decision support tools to help clinicians decide whether antibiotics are indicated, including the use of point-of-care tests, but acknowledge that further studies are required to ensure that system changes can be introduced without causing additional harm to patients.

A systematic review and cost-effectiveness analysis funded by the HTA evaluated PCT testing to guide antibiotic therapy for the treatment of sepsis in intensive care settings and for suspected bacterial infection in ED settings in adults and children [27]. The review concluded that addition of a PCT algorithm to the information used to guide antibiotic treatment may be a viable strategy to reduce antibiotic exposure in adults in ICU and ED settings without any adverse consequences and may also be associated with reductions in hospital and ICU stay in adults. None of the identified studies were conducted in the UK, and it was not clear whether

the control arms of these studies were representative of standard practice in the UK. The report recommended further studies of PCT to guide antibiotic treatment in adults with suspected or confirmed sepsis in ED settings, including research examining (short-term) health-state utility values. A recent patient level meta-analysis of randomised trials assessing the use of procalcitonin guided antibiotic treatment on outcomes for patients with infection and sepsis in intensive care settings suggests that procalcitonin use can significantly reduce mortality and antibiotic treatment duration [28]. A large prospective study of adult medical patients presenting to the ED demonstrated that admission PCT was a strong and independent predictor of 30-day mortality. The use of PCT in addition to qSOFA improved prognostic accuracy [29]. This suggests that PCT may help to improve risk stratification in suspected sepsis if combined with NEWS2.

The objective of this trial is not to prevent patients who require antibiotics from receiving antibiotics. It will assess whether by using NEWS2 and PCT, we can identify patients who require antibiotics within 1 hour whilst providing more time for clinicians to decide if antibiotics are required for patients who are less severely ill. It may therefore lead to less antibiotics and more narrow spectrum antibiotics being prescribed as clinicians may have more time to assess patients before they prescribe antibiotics. The rapid result of the PCT test, especially if it indicates a low or medium risk, may also provide reassurance to patients and families, and reduce anxiety.

5 Trial objectives/endpoints and outcome measures

